5.3. Control Treatment

Not applicable.

5.4. Dose Modification

Reducing or interrupting the dose for toxicity may take place at any time during the study according to the guidelines in Table 5.1 and Table 5.2. Dose modification guidelines for hematologic and hematologic treatment-related TEAEs are based on severity. Dose interruptions can be implemented at the discretion of the treating Investigator to manage intolerable or clinically significant toxicity. If a dose interruption is required, study assessments must be performed as scheduled, irrespective of the study drug delay, with the exception of PK assessments which must be deferred until treatment is resumed.

When an odd number of capsules are taken in a day, the larger number of capsules must be taken as the evening dose. For example, 600 mg/day = 3 capsules (1 capsule in the morning and 2 capsules in the evening). When an even number of capsules per day is to be taken, the morning and evening doses must be the same (eg, 800 mg/day = 4 capsules [2 capsules in the morning and 2 capsules in the evening] or 400 mg/day = 2 capsules [1 capsule in the morning and 1 capsule in the evening]).

Dose reductions must be applied in increments of 200 mg/day (1 capsule), with a maximum total reduction of 400 mg/day (ie, a minimum dose of 400 mg/day). Subjects unable to tolerate 400 mg/day (2 capsules) will be discontinued. Once dose reduction takes place for toxicity, a dose re-escalation is generally not allowed unless approved after discussion with the DS's Medical Monitor or designee.

Dose reduction	Total daily dose	Administration of total daily dose
First	600 mg	200 mg in the morning and 400 mg in the evening
Second	400 mg	200 mg twice daily

Table 5.1:Dose Modification

Dose modification guidelines for treatment-emergent toxicities as well as guidelines for their management are presented in Table 5.2. These parameters are only a guide and are not intended to supersede the clinical judgment of the treating Investigator. All adjustments must be communicated to DS's Medical Monitor or designee. Additional liver evaluation is presented in Table 5.3. Rechallenge with a reduced dose of pexidartinib may result in a recurrence of increased serum transaminases, bilirubin, or ALP. Monitor liver tests weekly for the first month after rechallenge.

Table 5.2:	Dose Modification	Guidelines for	Treatment-emergent Toxicities
-------------------	--------------------------	-----------------------	--------------------------------------

Adverse Reaction	Severity	Pexidartinib Dosage Modifications
Increased ALT and/or AST	Greater than 3 to 5 times ULN	 Withhold and monitor liver tests weekly. If AST and ALT are less than or equal to 3 times ULN within 4 weeks, resume at reduced dose. If AST or ALT is not less than or equal to 3 times ULN in 4 weeks, permanently discontinue pexidartinib. If AST or ALT is not less than or equal to 3 times ULN in 2 weeks, proceed to liver evaluation as outlined in Table 5.3
	Greater than 5 to 10 times ULN	 Withhold and monitor liver tests twice weekly. If AST and ALT are less than or equal to 3 times ULN within 4 weeks, resume at reduced dose. If AST or ALT is not less than or equal to 3 times ULN in 4 weeks, permanently discontinue pexidartinib. If AST or ALT is not less than or equal to 3 times ULN in 2 weeks, proceed to liver evaluation as outlined in Table 5.3
	Greater than 10 times ULN	 Permanently discontinue pexidartinib. Monitor liver tests twice weekly until AST or ALT is less than or equal to 5 times ULN, then weekly until less than or equal to 3 times ULN. Proceed to liver evaluation as outlined in Table 5.3

Increased ALP and Gamma-glutamyl transpeptidase (GGT)	ALP greater than 2 times ULN with GGT greater than 2 times ULN	 Permanently discontinue pexidartinib. Monitor liver tests twice weekly until ALP is less than or equal to 5 times ULN, then weekly until less than or equal to 2 times ULN. Proceed to liver evaluation as outlined in Table 5.3
Increased bilirubin	Total bilirubin greater than ULN to less than 2 times ULN or Direct bilirubin greater than ULN and less than 1.5 times ULN Total bilirubin greater or equal to 2 times ULN or Direct bilirubin greater than 1.5 times ULN	 Withhold and monitor liver tests twice weekly. If an alternate cause for increased bilirubin is confirmed and bilirubin is less than ULN within 4 weeks, resume at reduced dose. If bilirubin is not less than ULN in 4 weeks, permanently discontinue pexidartinib. If bilirubin is not less than ULN in 2 weeks, proceed to liver evaluation as outlined in Table 5.3 Permanently discontinue pexidartinib. Monitor liver tests twice weekly until bilirubin is less than or equal to ULN. Proceed to liver evaluation as outlined in Table 5.3
Adverse reactions or other laboratory abnormalities	Severe or intolerable	 Withhold until improvement or resolution. Resume at a reduced dose upon improvement or resolution.

ALT = alanine aminotransferase; ALP = alkaline phosphatase; AST = aspartate aminotransferase; GGT = gamma-glutamyl transpeptidase; ULN = upper limit of normal

Table 5.3: Additional Liver Evaluation

Evaluation	Instruction
Detailed history focusing on medications and substances used: alcohol, change in medication dosages, new medications added, attention to use of acetaminophen, OTC medication use and recreational drug use. Check for change in diet or use of dietary supplements with particular attention to dose and duration of any herbal product.	Suspect medications will be discontinued or substituted for if possible.
Detail medical history and physical examination seeking new abnormalities.	Evaluate any abnormalities found.
Full serological evaluation for hepatitis A, B, C, D, and E (IgG and IgM). Check for autoimmune hepatitis with serological laboratory studies.	If viral hepatitis or autoimmune hepatitis suggested, have subject evaluated by hepatologist.

Perform liver ultrasound to evaluate liver and biliary tree.	Evaluate any abnormalities found.	
Check history for exposure to chemical agents.	Remove chemical exposure and have subject seen by hepatologist.	
Obtain hepatology consult if liver function continues to rise beyond 14 day.	Contact Medical Monitor.	
Measure AMA.	Evaluate any abnormalities found.	
Perform liver biopsy to evaluate the pathological change (if possible).	Evaluate any abnormalities found.	
We request that cases be discussed with the Medical Monitor in instances where study drug is being		

held for liver function test abnormalities.

OTC = over-the-counter; AMA = anti-mitochondrial antibody

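### Section 5.4 puts all of Table 5.2 under Investigator judgment, so the protocol does not settle whether its six hepatic permanent-discontinuation entries are binding

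*Combined protocol and SAP*

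**What the plan says.** Section 5.4 introduces Table 5.2 as guidelines for dose modification and toxicity management, then adds: "These parameters are only a guide and are not intended to supersede the clinical judgment of the treating Investigator". The next sentence begins "All adjustments must be communicated to" and names the sponsor's Medical Monitor or designee.

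The hepatic entries in the table are written as orders. For ALT or AST above 10 × ULN the entry reads "Permanently discontinue pexidartinib. Monitor liver tests twice weekly until AST or ALT is less than or equal to 5 times ULN". The same order is given for "ALP greater than 2 times ULN with GGT greater than 2 times ULN" and for "Total bilirubin greater or equal to 2 times ULN or Direct bilirubin greater than 1.5 times ULN". The two lower transaminase bands carry a delayed stop: "If AST or ALT is not less than or equal to 3 times ULN in 4 weeks, permanently discontinue pexidartinib". The lower bilirubin band has an equivalent 4-week stop.

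Section 5.4 also contains a toxicity stop that is not subject to the guide sentence, "Subjects unable to tolerate 400 mg/day (2 capsules) will be discontinued", but it is not tied to a liver threshold. One action does need prior agreement: after a dose reduction, "a dose re-escalation is generally not allowed unless approved after discussion with the" Medical Monitor.

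**The concern.** Section 1.5 names liver toxicity as an important identified risk and acknowledges that it can kill or lead to transplantation. The numeric stops in Table 5.2 are the main subject-level protection against that outcome. A sentence that subordinates the whole table to individual judgment, without separating graded advice from absolute stops, leaves their force in doubt.

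Two things are at stake. An Investigator could continue drug at an immediate-stop value, or restart it after a failed 4-week recovery, and cite Section 5.4 as authority. Also, the approximately 10 to 15 sites could treat the same laboratory value differently, and the same decision could be logged as a protocol deviation at one site and as permitted judgment at another.

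**Working it through.** No stated figure is in dispute. The check is a count of the entries followed by a comparison of the sections that bear on them.

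**Step 1: count the stops in Table 5.2.**

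| Hepatic row | Permanent stop | What an override would be |
|---|---|---|
| ALT/AST >3 to 5 × ULN | 4 weeks without recovery | restart after a hold |
| ALT/AST >5 to 10 × ULN | 4 weeks without recovery | restart after a hold |
| ALT/AST >10 × ULN | immediate | unchanged dosing |
| ALP >2 × ULN with GGT >2 × ULN | immediate | unchanged dosing |
| Bilirubin, lower band | 4 weeks without recovery | restart after a hold |
| Bilirubin, upper band | immediate | unchanged dosing |

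Immediate: 1 + 1 + 1 = 3. At 4 weeks: 1 + 1 + 1 = 3. Total: 3 + 3 = 6. The seventh row, for other adverse reactions, has no permanent stop.

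**Step 2: ask which text governs.**

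- *Towards latitude:* the guide sentence in Section 5.4 covers the table as a whole and exempts nothing. Section 5.8.1 lists an adverse event among reasons a subject may be withdrawn, not must be.
- *Towards a binding stop:* the entries are imperative. The synopsis (Study Design; Dosage Form) has drug given until discontinuation criteria are met. It does not define those criteria, but the Table 5.2 entries are the only hepatic ones in the text. Section 14.5 forbids deviations from procedures and waivers of criteria, except to remove an immediate hazard, and names dosing among its examples of deviations.
- *Unhelpful either way:* the stop for unacceptable toxicity (synopsis, Section 3.1.1), which the supplied text does not define.

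If Section 5.4 prevails, 0 of the 6 stops are mandatory. If the table wording and Section 14.5 prevail, 6 of 6 are. No sentence ranks one above the other.

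**Step 3: count the controls around an override.**

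- *24-hour special-interest reporting (Sections 9.3.1 and 9.5):* ALT/AST above 3 × ULN covers 3 entries, ALP with GGT above 2 × ULN covers 1, and total or direct bilirubin above ULN covers 2. 3 + 1 + 2 = 6 of 6.
- *Liver work-up:* all 6 hepatic rows lead to Table 5.3, and Section 9.3.1 says that subjects meeting the Table 5.2 liver criteria will have the additional evaluations.
- *Duty to communicate adjustments (Section 5.4):* this is notice only. It reaches a restart after a hold, 3 of 6. It does not clearly reach unchanged dosing, the other 3.
- *Medical Monitor contact (Table 5.3):* contact is called for if liver tests keep rising beyond 14 days, and discussion is requested while drug is held. Neither is an approval.
- *Medical Monitor agreement before dosing continues or resumes:* 0 of 6. The re-escalation rule does not fill this gap, because restarting at a reduced dose is not a re-escalation.

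**Step 4: compare with the protocol's own practice.** Raising a reduced dose needs Medical Monitor approval (Section 5.4). Dosing past centrally confirmed progression before Week 25 needs the joint judgment of the Investigator and the Medical Monitor (Section 7.1.1). Dosing past a hepatic stop has no such requirement in the supplied text.

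**The case against.** The strongest reply is that the stops already bind. Section 14.5 prohibits deviations and waivers; it does more than ask for notice of them. An order to discontinue permanently at a numeric threshold can fairly be called a stated criterion. Where Section 5.4 expressly grants discretion, it does so in the protective direction, to interrupt dosing. No sentence expressly permits dosing past a permanent-stop entry. On this view the guide sentence is meant for judgment-dependent rows, such as the one for severe or intolerable reactions.

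Much of this stands. A reader might infer from the guide sentence that all 6 stops are simply advisory; the documents do not support that as a settled reading, for the reasons just given. The reply does not settle the opposite reading either. The orders sit inside the table that Section 5.4 subordinates to judgment, and Section 14.5 does not mention Table 5.2. An Investigator using discretion that the protocol grants is not clearly deviating from it.

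A reader might also infer that overrides would go unseen. That is not supported. The sponsor would learn of each event through the 24-hour report, and action taken on study drug is recorded with unchanged dosing as a category (Section 9.4.5). The Safety Monitoring Committee is set up to assess liver toxicity, and an external committee adjudicates hepatic events (Section 9.14). What remains is that nothing supplied requires any of these to act before the next dose.

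**Conclusion.** The point holds as an unresolved internal conflict, not as proof that the stops lack force. For 6 hepatic entries, 3 of them immediate, the supplied text leaves open whether the stop is mandatory, and it requires prior Medical Monitor agreement for none. Reporting, work-up and committee review are in place and limit the consequence.

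The conclusion rests on the supplied text. The charters of the two committees and the medical monitoring plan are separate documents and could contain subject-level stopping or consultation rules. No frequency is claimed: Section 1.3 reports liver-test abnormalities in earlier studies by event term and grade, not by Table 5.2 threshold, and nothing gives an override rate. The change is a cheap improvement, worth making because the harm at issue may be fatal.

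**What to change.** Add to Section 5.4, directly after the guide sentence, that it does not apply to the three immediate hepatic stops, which are mandatory: ALT or AST above 10 × ULN; ALP above 2 × ULN with GGT above 2 × ULN; total bilirubin at or above 2 × ULN or direct bilirubin above 1.5 × ULN.

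For the three 4-week non-recovery entries, choose one of two rules: make them mandatory as well, or require the Medical Monitor's documented agreement before dosing resumes. The second reuses a control that the protocol already applies to re-escalation. Either choice also makes clear when continued dosing counts as a deviation under Section 14.5.

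The change is to wording only. It alters no endpoint, visit or sample size. The cost is less Investigator latitude and possibly a few more recorded deviations.

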5.5. Method of Assessing Treatment Compliance

Pexidartinib will be dispensed to subjects at the study visits indicated in the Schedule of Assessment. The appropriate study personnel will document and maintain records of study drug dispensed to each subject and any returns at each study visit.

Subjects will complete a dosing diary to record the number of capsules/date/time the dose was taken during each dosing cycle.

At each site visit, subjects will be assessed for compliance with study drug administration, ie, actual capsules taken/expected capsules taken. The subject must also return all bottles (used/unused) at each dispensing visit.

Further details can be found in each manual.

5.6. Prior and Concomitant Medications

During the study, if the use of any concomitant treatment becomes necessary (eg, for treatment of an AE), the treatment must be recorded on the source document and electronic Case Report Form (eCRF), including the reason for treatment, name of the drug, dosage, route, and date of administration. All medications including prescription, over-the-counter (OTC), herbal and other nutritional vitamins and/or supplements taken within 28 day of C1D1 will be recorded on the eCRF. Analgesic use and analgesic regimen will be recorded.

Subjects enrolled in studies with pexidartinib and are receiving concomitant warfarin must have their anticoagulation status carefully monitored, especially shortly after initiation of pexidartinib, for the potential need to make adjustments in warfarin dosing. In particular, international normalized ratio (INR) must be obtained just prior to initiation of pexidartinib, within 1 to 2 weeks after initiation, and periodically thereafter. Dose adjustments of warfarin must be made as medically indicated.

Avoid the concomitant use of pexidartinib with other products known to cause hepatotoxicity.

5.6.1. CYP3A inducers

Avoid the concomitant use of strong CYP3A inducers, including St John's wort (see Section16.1, a list of common CYP3A inhibitors and inducers).

5.6.2. CYP3A and UGT inhibitors

Avoid concomitant use of pexidartinib with moderate or strong CYP3A inhibitors or UDPglucuronosyltransferase (UGT) inhibitors during treatment with pexidartinib. If concomitant use with a moderate or strong CYP3A inhibitor or UGT inhibitor cannot be avoided, reduce the pexidartinib dose according to the recommendations in Table 5.4. If concomitant use of a moderate or strong CYP3A inhibitor or UGT inhibitor is discontinued, increase the pexidartinib dose (after 3 plasma half-lives of the moderate or strong CYP3A inhibitor or UGT inhibitor) to the dose that was used before starting the inhibitor.

Table 5.4:Recommended Dosage Reductions for Pexidartinib for Concomitant Use of
Moderate and Strong CYP3A Inhibitors or UGT Inhibitors

Planned Total Daily Dose	Modified Total Daily Dose	Administration of Modified Total Daily Dose
800 mg	400 mg	200 mg BID
600 mg	400 mg	200 mg BID
400 mg	200 mg	200 mg once daily

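### Section 5.6.2 restores the pre-inhibitor dose with no exception for toxicity on the inhibitor, which in two situations conflicts with Section 5.4 and Table 5.2

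*Combined protocol and SAP*

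**What the plan says.** Four parts of protocol Section 5 bear on the dose of a subject who has taken an inhibitor and had toxicity.

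- **Section 5.6.2.** Moderate or strong CYP3A inhibitors and UGT inhibitors are to be avoided. If one is unavoidable, the site must "reduce the pexidartinib dose according to the recommendations in Table 5.4". That table maps planned daily doses of 800, 600 and 400 mg to 400, 400 and 200 mg, the last given as "200 mg once daily". Three inhibitor half-lives after the inhibitor stops, pexidartinib is increased "to the dose that was used before starting the inhibitor".
- **Section 5.4, re-escalation.** "Once dose reduction takes place for toxicity, a dose re-escalation is generally not allowed unless approved after discussion with the DS's Medical Monitor"; a designee may stand in.
- **Section 5.4, minimum dose.** Reductions go in 200 mg/day steps, "with a maximum total reduction of 400 mg/day (ie, a minimum dose of 400 mg/day"). A subject who cannot manage that floor stops treatment: "Subjects unable to tolerate 400 mg/day (2 capsules) will be discontinued".
- **Tables 5.2 and 5.3.** For ALT or AST above 3 and up to 10 times ULN, drug is withheld, and it is restarted at a lower dose if values recover within 4 weeks. If they have not recovered at 2 weeks, the Table 5.3 work-up begins. Part of that work-up is stopping or replacing suspect co-medication where possible.

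Sections 5.4 and 5.6.2 do not refer to each other on this point, and neither is given precedence.

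**The concern.** Section 5.6.2 names its target as a dose from the past: whatever the subject took before the inhibitor. That dose necessarily predates any toxicity on the inhibitor, and the sentence has no exception for it. Section 5.4 treats a toxicity reduction as something that normally stays in place. A site can therefore follow one section and depart from the other.

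What is at stake is hepatic safety. Section 1.5 calls liver toxicity an important identified risk and says that it may be fatal. The approval step in Section 5.4 controls upward moves after toxicity, and Section 5.6.2 describes an upward move without it. The extra liver monitoring has the same gap. "Monitor liver tests weekly for the first month after rechallenge" follows a sentence about rechallenge at a reduced dose, and nothing ties it to the Section 5.6.2 increase.

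**Working it through.** The protocol states no figure to reproduce. The check sets the rules side by side and follows the dose through each order of events.

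**Inputs (mg/day).** Starting dose 800 (Section 3.1). Toxicity ladder 800 → 600 → 400, then discontinuation (Section 5.4, Table 5.1). Inhibitor adjustment 800 → 400, 600 → 400, 400 → 200 (Table 5.4). Every inhibitor-adjusted dose is therefore at or below the 400 minimum.

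**The base for the toxicity step is not stated.** Table 5.2 says to restart lower, but not whether the step is taken from the planned dose or from the inhibitor-adjusted dose. Take a subject on 800 before the inhibitor:

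| Order of events | Section 5.6.2 after the inhibitor stops | Section 5.4 and Table 5.2 | Conflict |
|---|---|---|---|
| (a) Toxicity on the inhibitor, step counted from the planned dose (800 − 200 = 600) | 800 | 600, unless an increase is approved | Yes |
| (b) Liver hold, and the inhibitor is stopped during the hold | 800 | A reduced dose (600 if one step from the planned dose) | Yes |
| (c) Toxicity on the inhibitor, step counted from the adjusted dose (400 − 200 = 200) | Not reached if the subject is discontinued | 200 is below the minimum, so there is no lower step | Different gap |
| (d) Toxicity reduction to 600 made before the inhibitor | 600 | 600 | No |

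**Situation (a).** The two doses differ by 800/600 = 1.33, that is, 33% higher under Section 5.6.2. Two toxicity steps counted from the planned dose would give 800/400 = 2.0. Table 5.4 offers some support for counting this way: its first column is the planned daily dose, and it has rows for 600 and 400. The reading is not clean, however. Planned 800 and planned 600 both map to 400 on an inhibitor, so one step from the planned dose does not change what the subject takes while the inhibitor continues. Table 5.2 nevertheless calls for a lower dose on restart.

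**Situation (b).** The protocol's own liver pathway can produce this. A hold lasting beyond 2 weeks leads to Table 5.3, where the inhibitor may be stopped as a suspect medication. Recovery within 4 weeks then permits a restart. Stopping the inhibitor triggers the Section 5.6.2 increase, and the recovery triggers the reduced restart of Table 5.2.

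**Situation (c).** Table 5.2 tells the site to restart lower, while Section 5.4 allows nothing lower and discontinues a subject who cannot tolerate 400. Table 5.4 itself lists 200, and the protocol does not say whether the Section 5.4 minimum covers inhibitor adjustments. This is a separate inconsistency and does not resolve the first.

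**Monitoring of the increase.** After Week 25 the continuation schedule in Section 16.6 lists liver tests on Day 1 of every third cycle: 3 × 28 = 84 days, or 12 weeks. Unless the weekly tests of Section 5.4 are held to apply, an increase in that period could precede the next scheduled test by up to about 12 weeks.

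**The case against.** The strongest reply is that the two sections can be read together. Section 5.6.2 sits under concomitant medication and reverses an interaction adjustment. Section 5.4 governs toxicity, and its limit on re-escalation has no carve-out for inhibitor cases. A careful site would undo only the interaction step and seek approval before reversing a toxicity step. That reading is sensible, but it is not written down. Section 5.6.2 does not say to undo the adjustment; it specifies the dose to return to.

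Three further points stand in part.

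- **The minimum dose narrows the problem.** A reader might infer that any subject reduced for liver toxicity while on an inhibitor can be put back on the full dose. The documents do not support that. If the step is counted from the dose actually taken, a subject already at 400 mg/day has no lower step and, on a literal reading of Section 5.4, is discontinued. If the reduction came before the inhibitor, nothing conflicts. The full 800 mg/day is in question only if that was the pre-inhibitor dose.
- **There is oversight.** A reader might infer that the increase happens without review. That goes too far. Section 5.4 requires every adjustment to be communicated to the Medical Monitor, and Table 5.3 asks that liver holds be discussed with that person. Section 9.5 requires ALT or AST above 3 times ULN to be reported within 24 hours. A safety monitoring committee and a hepatic adjudication committee are also in place (Section 9.14). None of these is the approval step that Section 5.4 attaches to re-escalation.
- **The rules are not rigid.** Section 5.4 permits approved re-escalation and describes the Table 5.2 parameters as a guide that does not override clinical judgment. With approval both sections could arrive at the same dose; the remaining difference is whether approval is needed.

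**Conclusion.** The inconsistency is real but confined to situations (a) and (b). There, for a subject on 800 mg/day before the inhibitor, Section 5.6.2 points to 800 mg/day, while Section 5.4 and Table 5.2 point to a reduced dose, 600 mg/day after one step from the planned dose. The twofold gap needs two toxicity steps and the planned-dose reading. Situation (c) is a related gap among Section 5.4, Table 5.2 and Table 5.4.

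The number of subjects affected cannot be estimated. The protocol gives no rate of inhibitor use and no rate of qualifying toxicity during such use. The AST and ALT figures from the earlier Phase 3 study in Section 1.3.2 (35.2% and 28.6%) are not broken down by the Table 5.2 thresholds or by inhibitor use, so they cannot supply one. With about 35 subjects and inhibitors to be avoided, the number is probably small.

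A reader might also infer that the exposure or hepatic summaries would be compromised. Section 10.4 plans only descriptive exposure summaries, and no planned analysis can be shown to depend on this rule. The case for acting rests on the severity of the possible harm and the low cost of clearer wording.

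**What to change.** Reconcile the last sentence of Section 5.6.2 with the re-escalation and minimum-dose sentences of Section 5.4 and with Tables 5.2 and 5.4, so that one stated rule governs a subject who had a toxicity hold or reduction while on an inhibitor. The text should state:

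- whether the toxicity step is counted from the planned or the inhibitor-adjusted dose;
- whether the 400 mg/day minimum applies to inhibitor adjustments, given the 200 mg row of Table 5.4;
- which section prevails when the inhibitor stops during a liver hold;
- whether the Medical Monitor approval and the weekly liver tests of Section 5.4 apply to the Section 5.6.2 increase.

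The choice of dose and rule belongs to the sponsor's clinical team. The cost is a few sentences and a cross-reference in the next amendment or a dosing clarification letter, with no extra subjects. If the weekly tests are held to apply, the subjects concerned would have those additional blood draws.
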